1.1 Study rationale and justification

1.1.1 Current status of breast cancer in western countries

Breast cancer is the most common cancer and the second leading cause of cancer death among women in Western countries. Breast cancer (BC) is a dramatic worldwide issue with almost 1.7 million new BC diagnoses and 521,900 BC deaths estimated worldwide in 2012 <https://www.ncbi.nlm.nih.gov/pubmed/28376154>.

Breast cancer remains a potentially lethal disease. Indeed, 20 to 25% of women developing breast cancer will eventually die, due to the development of metastases. Risk of metastases and global prognosis are linked to both tumor biology and burden at diagnosis (Cardoso 2016).

Although very long survivals are sometimes possible, metastatic breast cancer remains an incurable disease. The median survival after diagnosis of metastases currently ranges from 14 months (triple-negative breast cancers) to 56 months (Her2-positive breast cancers) (Gobbini 2018).

Localized breast cancer currently most of the time still requires aggressive and prolonged treatments associated with long-term consequences (Azim 2011). Treatment intensity and heaviness is clearly deeply linked to the cancer's biology, but also to tumor burden at diagnosis. Tumor burden is the major determinant of the extent of the local therapies, including surgery (partial versus complete mastectomy, axillary surgery) and radiation therapy. Adjuvant medical treatments for breast cancer, including chemotherapy, endocrine and targeted therapies remain difficult for women; they are associated with long-term sequelae, and represent high management costs (Azim 2011).

There is therefore a major need for prevention, including earlier diagnosis (associated with a better prognosis, less treatments needs, less morbidity from the therapies, and lower costs) through secondary prevention, but also, of course, primary prevention.

1.1.2 **Current breast cancer screening in western countries: benefits and potential harms, evaluation, organization**

Current breast cancer screening policies in western countries and known benefits

In Western countries, breast cancer screening is part of national organized screening systems with monitoring of screening quality and with double reading (except in Israel) of the mammograms. Certified radiologists and radiographers are responsible for quality of the diagnostic performance.

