1.1.24 Rationale for evaluation of PROs in MyPeBS

Refs: Lerman, Hersch, Martinez-Alonso, O'Donnel, Fox, Morman, Johansson, Wardle

As mentioned previously, there are number of potential human costs to implement the communication of risk information on such a scale as in MyPeBS trial. This includes possible undue worry and anxiety for women at high-risk, a lack of informed decision making regarding treatment options, reduction in mammography attendance, false reassurance in those at low-risk, resulting in subsequent nonattendance at screening and lack of attendance to health-related behaviors that place women at increased risk. The existing literature suggests that many of these harms are not likely, but evidence is not compelling.

The very careful evaluation of participants' related outcomes (PROs) is therefore a key component of MyPeBS trial.

The overall methodology of participants' reported outcomes measures (PROs) in the present trial is based on online questionnaires (exceptionally paper questionnaires). In MyPeBS, we use validated well-known questionnaires, except for very specific purposes (e.g., comprehension or satisfaction with specific documents...), for which dedicated questionnaires have been developed and validated with a group of patient's advocates, healthcare professionals and researchers.

Comprehension of information provided

Based on the information tools used, we have developed a comprehension questionnaire containing true/false questions divided into three categories of information provided:

- (1) General information on breast cancer;
- (2) Information on breast cancer risk;
- (3) Information on benefits and risks of breast cancer screening.

The main reasons for using this type of questionnaire are:

- Data obtained using true/false questions are easy to analyze as compared to questionnaires containing open-ended questions
- This type of questionnaire provides a better comprehension assessment of the information provided as compared to a questionnaire based only on the comprehension feeling

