3.2.2 Secondary endpoint(s)

SECONDARY ENDPOINT(S): (All at 4 years/during intervention period unless otherwise indicated):

1. Rates of false positive imaging findings and benign biopsies in each study arm
 - False positive imaging findings include BI-RADS-ACR 3, 4 and 5 (or equivalent) lesions identified on screening images and leading to the need of additional images (US, MRI...), later control or breast biopsy
 - Benign biopsies include any percutaneous or surgical breast diagnostic procedure aimed at identifying the nature of a breast image
2. Socio-psychological assessments at baseline, and then at 1 and 4 years including evaluation of: comprehension of information, acceptance of proposed screening strategy, observance, persistence, anxiety, distress, satisfaction, decisional regret (see questionnaires in table 1)
3. Crude costs, comparison of cost-effectiveness, and budget impact of each strategy
 - Crude costs are defined as full real costs per stage 2 cancer diagnosis in each arm
 - The cost-effectiveness of mammographic screening will be calculated by comparing estimated life-years and costs of breast cancer in each arm
4. Incidence of stage-specific breast cancer in each arm (including DCIS)
5. Estimates of overdiagnosis and overtreatment rates in each study arm
 - Overdiagnosed breast cancer cases are defined as cancers that would never have been diagnosed, if women had not been screened. Differential overdiagnosis can be measured comparing the cumulative incidence of breast cancer from recruitment to a reasonably long period after the end of the study intervention, i.e. longer than the expected sejour time of screen-detected cancers. Breast cancer incidence rates in each arm will be determined approximately 10 - 15 years after the end of the interventional period of the study via interrogation of databases from national health insurances and/or organized breast screening structures.
6. Rate of false negative images and interval cancers in each arm
 - False negative images: in case of diagnosis of breast cancer in women whose last screening images (including mammogram +/- US and MRI) were considered as Breast Imaging- Reporting and Data System 1 or 2 (BI-RADS 1 or 2) at 6 months maximum before diagnosis

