Appendix 4: Participants' questionnaires

The following questionnaires will be used in this study:

- Socio-demographic and economical status questionnaire
- Comprehension questionnaire
- STAI short form (state anxiety)
- Quality of life (EQ-D)

TABLE 1 – SOCIO-PSYCHOLOGICAL QUESTIONNAIRES

VISITS	Baseline	Risk-based screening arm	Follow-up	
Visits n°	Visit (V0)	V1	NA	NA
Visit Dates	D0	V0 + 8-12 weeks	M12 +/- 6 months	M48 +/- 6 months
Type of visit	physical	physical or telephone call	On-line	On-line
QUESTIONNAIRE				
1. STAI short form (state anxiety)	X	X	X	X
2. Comprehension questionnaire	X	X		X
3. Information seeking-behavior questionnaire		X		X
4. Quality of life (EQ-5D)	X			X
5. Satisfaction			X	X
6. Socio-demographic and economical status questionnaire	X			X

STAI short form

A number of statements which people have used to describe how they feel are given below. Please read each statement and then circle the most appropriate number to the right of the statement to indicate how you feel right now, at this moment. There are no right or wrong answers. Do not spend too much time on any one statement but give the answer which seems to describe your present feelings best.

	Not at all	Somewhat	Moderately	Very much
1. I feel calm	1	2	3	4
2. I am tense	1	2	3	4
3. I feel upset	1	2	3	4
4. I am relaxed	1	2	3	4
5. I feel content	1	2	3	4
6. I am worried	1	2	3	4

Comprehension & Information seeking-behaviour questionnaire

Comprehension

Frequency : Baseline, +3/5m, +4y

Below are some questions about breast cancer screenings. Some sentences are true, others are false. Take your time, and for each question, please circle the answer that you think is correct.

Circle only one answer

TRUE

FALSE

BREAST CANCER

1. Breast cancer is the most common cancer for women in occidental country
2. We can always cure breast cancer

BREAST CANCER SCREENINGS

3. Screening makes it possible to detect cancer as early as possible before it gives symptoms
4. The sooner you detect breast cancer, the easier it is to heal it
5. Mammography screening consists of making a breast x-ray on a regular basis
6. Stratified screening relies on a saliva sample to analyse DNA
7. Calculating individual risk include information on age, family history of cancer, biopsy history, breast density

BREAST CANCER SCREENINGS' BENEFITS AND RISKS

1. Mammography can be painful.
2. Breast cancer screening reduces breast cancer mortality by an average of 20%. In other words, it avoids 1 out of 5 deaths.

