3. Sometimes, breast cancer screening can detect a non cancerous tumor that leads to exams, such as a biopsy to know whether

the tumor is cancerous or not.

4. Sometimes, breast cancer screening can lead to over-diagnosis, that is it detects a tumor that that does not progress to cancer and thus lead to unnecessary treatments (surgery, chemotherapy, radiotherapy).
5. Stratified screening allows the adaptation of the frequency of screening tests according to the individual risk of each woman
6. Stratified screening allows women at higher risk of breast cancer to benefit from more intensive exams with different techniques
7. Stratified screening allows women at low risk of breast cancer to do screening less often

Information seeking-behaviour questionnaire

Frequency : +3/5m, +4y

1. Did you search for information on breast cancer screening (please check on box)
Yes
No
2. If yes, did you search in/on :
 - Internet :
 - o Cancer websites (NCI, comprehensive cancer centers)
 - o General websites (Google, Bing, Yahoo etc.)
 - Libraries
 - Medical articles
 - Mass media
 - Ask questions to healthcare professionals (GP etc.)
 - Ask questions to family and friends
 - Others please specify :
3. If yes, did you search for information focused on stratified breast cancer screening?
Yes
No
4. If no,
 - a. Did you search for information on organized breast cancer screening?
 - b. Did you search for information on breast cancer ?
 - c. You did not search for information at all

Quality of life

EQ-5D questionnaire.

Frequency : Baseline, +4y

Q1. Mobility

1. I have no problems in walking about
2. I have slight problems in walking about
3. I have moderate problems in walking about
4. I have severe problems in walking about
5. I am unable to walk about

Q2. Self-care

1. I have no problems washing or dressing myself
2. I have slight problems washing or dressing myself
3. I have moderate problems washing or dressing myself
4. I have severe problems washing or dressing myself
5. I am unable to wash or dress myself

Q3. Usual activities (e.g. work, study, housework, family or leisure activities)

1. I have no problems doing my usual activities
2. I have slight problems doing my usual activities
3. I have moderate problems doing my usual activities
4. I have severe problems doing my usual activities
5. I am unable to do my usual activities

Q4. Pain/discomfort

1. I have no pain or discomfort
2. I have slight pain or discomfort
3. I have moderate pain or discomfort

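### By content, 13 of the 14 comprehension statements are true (12 on the strictest keying) and there is no 'don't know' option, so agreement cannot be told apart from understanding in the two screening domains

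*Protocol*

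**What the plan says.** Protocol Section 3.2.2, secondary endpoint 2, lists the socio-psychological constructs to be assessed: "comprehension of information, acceptance of proposed screening strategy, observance, persistence, anxiety, distress, satisfaction, decisional regret". Section 1.1.24 describes the tool for the first of these as "a comprehension questionnaire containing true/false questions divided into three categories of information provided". It justifies the format partly on the ground that it tests understanding better than asking women whether they feel they understood. The same section says that the trial-specific questionnaires were developed and validated with patient advocates, professionals and researchers. It also plans to relate comprehension to information-seeking and to women's socio-economic and demographic characteristics.

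Appendix 4 prints the instrument. It has three headings: breast cancer (2 statements), breast cancer screening (5), and benefits and risks of screening (7). The instruction reads "Some sentences are true, others are false", and one of two answers, TRUE or FALSE, is to be circled. The first heading contains "We can always cure breast cancer"; the last statement under the third is "Stratified screening allows women at low risk of breast cancer to do screening less often". The form is given at baseline, at the second visit in the risk-based arm, and at 4 years.

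The protocol prints no answer key, total score, domain score or pass mark. Section 8.6.2 refers the socio-psychological evaluation to a work package of the wider project.

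**The concern.** A true/false test separates knowledge from a habit of agreeing only if some statements must be rejected. The instruction leads the respondent, and a later reader of the results, to expect a mixed set. If nearly every statement is true, a woman who agrees with everything looks almost the same as one who understands everything.

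Two uses of the result are affected. The first is the absolute level: a high percentage correct could be read as showing that participants were well informed. The second is any comparison between arms, between baseline and 4 years, or between socio-economic groups, where differences in knowledge would appear smaller than they are.

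This is not a matter that an analysis plan can settle. The wording and the response options are fixed in the protocol, and no analysis can recover answers to false statements that were never asked.

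**Working it through.** The plan states no score to reproduce, so the check is to key the items, score an all-TRUE respondent, and then vary the tendency to answer TRUE.

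**Step 1: key the 14 statements on content.**

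- *Breast cancer (2).* Item 1, on frequency, is true; compare Section 1.1.1: "Breast cancer is the most common cancer and the second leading cause of cancer death among women in Western countries". Item 2, "We can always cure breast cancer", is false; the same section says "metastatic breast cancer remains an incurable disease".
- *Screening (5).* Two items say what screening and a mammogram are, and are true by ordinary meaning. The item on the advantage of early detection agrees with Section 1.1.1, the saliva and DNA item with Sections 5.2.1 and 5.2.2, and the risk-input item with Section 5.2.3. All 5 are true. Section 5.2.3 allows risk to be estimated without genotyping when that is unavailable or refused, but saliva is the planned basis, so the saliva item is keyed true.
- *Benefits and risks (7).* The 20% mortality item agrees with Section 1.2.1 and the benign-finding item with Section 1.1.2. The three items on adapting screening to risk agree with Section 5.2.5. The pain item has no support elsewhere in the protocol but only says that pain can occur. The over-diagnosis item speaks of a tumour that never becomes cancer, whereas Section 1.1.2 speaks of a cancer that would not have surfaced clinically. It is evidently meant as true but is arguable. So 7 are true, or 6 on the strict reading.

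Total true: 1 + 5 + 7 = 13 of 14. Strict reading: 1 + 5 + 6 = 12 of 14.

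**Step 2: score an all-TRUE respondent (number correct, assumed).**

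| Domain | Main keying | Over-diagnosis keyed false |
|---|---|---|
| Breast cancer | 1/2 = 50% | 1/2 = 50% |
| Screening | 5/5 = 100% | 5/5 = 100% |
| Benefits and risks | 7/7 = 100% | 6/7 = 86% |
| All items | 13/14 = 93% | 12/14 = 86% |

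With seven true and seven false items she would score 7/14 = 50%.

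**Step 3: let a woman who does not know an item answer TRUE with probability p.** Nothing in the protocol gives p. Her expected score is

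g(p) = [13p + (1 − p)]/14 = (12p + 1)/14.

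If a further 20% of items become known, the score rises by 0.20 × (1 − g).

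| p (assumed) | g, printed form | 20 points shows as | g, balanced key | 20 points shows as |
|---|---|---|---|---|
| 0.5 | 7.0/14 = 50.0% | 10.0 | 50% | 10.0 |
| 0.7 | 9.4/14 = 67.1% | 6.6 | 50% | 10.0 |
| 0.9 | 11.8/14 = 84.3% | 3.1 | 50% | 10.0 |

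With the over-diagnosis item keyed false, g = (10p + 2)/14. That gives 64.3% and 7.1 points at p = 0.7, and 78.6% and 4.3 points at p = 0.9.

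**The case against.** Several counter-arguments carry weight.

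- **No scoring rule is printed.** Percentages correct, overall or by domain, are therefore an assumption. If results are reported item by item, the 93% never appears. This stands, but the imbalance in the items does not depend on the scoring.
- **The loss depends on p.** At p = 0.5 the printed form loses nothing against a balanced one, and telling women that some statements are false works against blanket agreement. This stands; the 6.6 and 3.1 points are illustrations.
- **Misconceptions are still caught.** A reader might infer that the form measures only readiness to agree, or that scores sit at the ceiling whatever women understand. The documents do not support that. A woman who believes that screening has no harms, or that women at low risk are not screened less, answers FALSE and is marked wrong.
- **The trial is large.** A reader might also infer that a difference between arms would be hidden. With 42,500 women per arm and the largest possible SD of a 0–100 score (50), the standard error is 50 × √(2/42,500) = 0.34 points, so 3.1 points is about 9 standard errors. If only 10% respond (assumption), it is 50 × √(2/4,250) = 1.08 points, and 3.1 points is still about 2.9. Randomisation also balances answering style at baseline, and a style that is equal in both arms masks a difference rather than creating one. So the difference is shrunk, not necessarily lost. Detecting it does not restore its size or correct the absolute level.
- **The questionnaire was validated.** Section 1.1.24 says so, but the evidence is not shown, and such a review does not change which statements are true.

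**Conclusion.** The point holds as a weakness of the instrument. The screening domain contains no false statement, and the benefits-and-risks domain contains none or at most one. In these two domains agreement cannot be separated from understanding. Under number-correct scoring, an all-TRUE respondent reaches 93% overall, or 86% on the strictest keying of the over-diagnosis item. Absolute levels are inflated and differences attenuated to the extent that women who do not know lean towards TRUE. That extent is unknown.

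The conclusion rests on keying by content and, for the percentages, on number-correct scoring. It does not show that the form fails to measure comprehension at all, nor that the two domains must be left unreported. It concerns one component of secondary endpoint 2; the primary and key secondary analyses are untouched. It is worth correcting because the change is small and because this form was chosen to be more objective than self-rated comprehension.

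**What to change.** **If the form has not yet been used:** reverse about half the statements in each domain so that the correct answer is FALSE. Going from 13 true statements to 7 means rewording about six. The protocol's own awareness messages in Section 5.2.6 supply material by negation, for example a statement that a mammogram finds every cancer, or that low risk means no risk. Add a 'don't know' option scored as not correct, and reword the over-diagnosis item so that its key is not in doubt.

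**If collection has begun:**

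- Keep the existing items unchanged, so that the comparison of baseline with 4 years survives.
- Add a few false-keyed items per domain, with a version flag.
- Report true-keyed and false-keyed items separately.
- Report the existing screening and benefits-and-risks domains item by item, with a caveat, and not as evidence of high comprehension.

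**Cost:** rewording and re-translating a few short online items. The new items will have limited comparability with earlier assessments.

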In addition, it is important to understand the reasons for any increases in distress in the risk-stratified screening groups, as it may be an intrinsic result of receiving risk feedback, or it may be more modifiable effects of the healthcare system. For this reason, we will conduct - in England and France only - a qualitative assessment with up to 24 women who undergo risk-stratified screening. They will be interviewed three months after receiving their risk estimation results. They will be purposively sampled to ensure variation in risk results received, and variation in socio-economic status. They will be asked about how acceptable they found the process, what they understood was the purpose of each element of the screening process, if they would recommend the process to their friends, and how the process could be improved. A matched sample of 16 women in the same countries who declined to participate to the trial will be interviewed to assess their views of this form of screening, and what they found to be not acceptable about it. Data analysis will use a manifest level approach to thematic analysis.

Participants' satisfaction

We will use a questionnaire assessing decisional satisfaction and regret regarding trial participation using the satisfaction with decision scale (SWD) and the decisional regret scale (DRS), respectively. The 6-item SWD scale has good reliability and discriminant validity (Holmes-Rovner et al, 1996). The DRS is a widely used 5-item scale with good internal consistency (Brehaut et al, 2003).

In terms of trial-related behavior, intention to participate in the trial will be assessed after the trial participation decision had been made at 1 year and that actual enrolment and subsequent dropout were recorded at the end of their participation at 4 year. We will assess the differences between both arms using equality of proportion and chi-square tests.

Furthermore, we will assess participants' satisfaction regarding care received during the trial, in both arms. For this purpose, we will adapt the Sat-35 questionnaire by using only appropriate items, as previously described.

To be as close as possible to women concerns, this work will be developed and conducted in close collaboration with patients' associations and advocates, particularly ICPV and the European Cancer leagues.

Impact of socio-economic status

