2.2 Secondary objective(s)

(ALL AT 4 YEARS/DURING INTERVENTION PERIOD UNLESS OTHERWISE INDICATED)

1. The key secondary objective, if non-inferiority is shown, is **to demonstrate superiority** of the risk-based screening arm to reduce the incidence rate of stage 2+ breast cancer, compared to standard screening.

2. To compare the rate of morbidity between the two arms, in terms of false positive imaging findings and benign biopsies
3. To describe the psycho-social characteristics of the population accrued and evaluate the psycho-social impact of each strategy (acceptance, observance, anxiety, distress, satisfaction, decisional regret, etc.)
4. To evaluate the costs and cost-effectiveness of each strategy
5. To evaluate the stage-specific incidence of breast cancer of any stage in each arm
6. To estimate overdiagnosis and overtreatment rates in risk-based screening and standard screening arms
7. To compare the rate of false negative mammograms and interval cancers between arms
8. To evaluate superiority of risk-based screening in terms of breast cancer-specific mortality at 10-years and 15-years in MyPeBS and in a combined analysis of the Wisdom and MyPeBS studies
9. To evaluate the added value of tomosynthesis (TS) in the detection of stage 2+ breast cancers
10. To evaluate the incidence of all stage and stage 2+ breast cancers at 10- and 15-year follow-up
11. To evaluate the incidence of stage 2+ breast cancer in risk-based screening in women aged 40-50 years old as compared to standard screening
12. To evaluate the rate of breast cancers discovered at second reading in each arm
13. To evaluate false positive imaging findings and benign breast biopsy rates in women classified in the low risk category in risk-based arm

EXPLORATORY OBJECTIVES (ALL AT 4 YEARS/DURING INTERVENTION PERIOD UNLESS OTHERWISE INDICATED):

1. To evaluate the added value of ultra-sound in the detection of stage 2+ breast cancers in each arm
2. To describe and compare between the arms, the rates of breast cancer predicted at 10- and 15-year, metastatic risk >10% using validated clinical-pathological predictors and the rates of cancers requiring chemotherapy
3. To explore the efficacy and morbidity of risk-based screening versus standard screening in subgroups (including country, risk and age categories)

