4. I have severe pain or discomfort
5. I have extreme pain or discomfort

Q5. Anxiety/depression

1. I am not anxious or depressed
2. I am slightly anxious or depressed
3. I am moderately anxious or depressed
4. I am very anxious or depressed
5. I am extremely anxious or depressed

Trial Program Satisfaction

This questionnaire will include an evaluation of the overall satisfaction of women to participate to the study with the two screening strategies (information, communication tools, organization of the screening). The intention to participate in the study will be assessed after the study participation decision had been made at 1 year and that actual enrolment and subsequent dropout were recorded at the end of their participation at 4 year. We will assess the differences between both arms using equality of proportion and chi-square tests.

We have selected and modified questions of a satisfaction questionnaire on organization of the screening process and the information received validated by Bairati & al (2014) and use actually in Canada (<https://www.ncbi.nlm.nih.gov/gate2.inist.fr/pmc/articles/PMC3893508/>)

Frequency : 1y, +4y

7 questions with answer according a 5 points scale

You are involved in MyPeBS a breast cancer screening clinical study. Could you please answer the following questions about your satisfaction. Please indicate for each statement to what extent you agree or disagree now.

Use the following scale to answer the questions.

1 = strongly disagree

2 = disagree

3 = neither agree nor disagree

4 = agree

5 = strongly agree

1. The decision to participate to My PeBS clinical study was a good decision for me.
2. I regret to participate (or to have participated) in MyPeBS study because the medical follow-up does not correspond to what I expected.
3. I regret to participate (or to have participated) to MyPeBS study because the anxiety generated is greater than I expected.
4. I am satisfied with the information I received in the documents on the pros and cons of participating in MyPeBS study.
5. I am satisfied by the clarity of the information given in MyPeBS documents to present the study (informed consent and information sheets).
6. I am satisfied with the explanations given by health professionals about what happens for me at each stage of MyPeBS study (different exams and their rhythm)
7. I am satisfied by the personal information offered by the web-platform dedicated to MyPeBS study.

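### Section 1.1.24 names the SWD and DRS for decisional satisfaction and regret, but Table 1, the schedule and Appendix 4 collect only one 7-item form from which neither scale can be scored

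*Protocol*

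**What the plan says.** Section 1.1.24, under participants' satisfaction, states that decisional satisfaction and regret about trial participation will be assessed "using the satisfaction with decision scale (SWD) and the decisional regret scale (DRS), respectively". It supports each choice by its measurement properties: "The 6-item SWD scale has good reliability and discriminant validity", and "The DRS is a widely used 5-item scale with good internal consistency". For satisfaction with care it names a third source: "we will adapt the Sat-35 questionnaire by using only appropriate items, as previously described".

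Secondary objective 3 in section 2.2 lists the psycho-social outcomes as "acceptance, observance, anxiety, distress, satisfaction, decisional regret, etc". Secondary endpoint 2 in section 3.2.2 repeats "satisfaction, decisional regret (see questionnaires in table 1" and so sends the reader to Table 1 for the instruments.

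Table 1 (in the synopsis, and again in Appendix 4) and the schedule of activities have a single row called Satisfaction, ticked at M12 and M48. Neither has a row for the SWD or the DRS. Appendix 4, under trial program satisfaction, prints the form behind that row: "7 questions with answer according a 5 points scale". It says that the items were selected and modified from a validated questionnaire on how screening is organised and what information is given. It does not mention the SWD or the DRS.

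**The concern.** The section that justifies the patient-reported outcomes promises two validated scales, while the sections that determine what women are asked contain neither. Sites and the web platform will work from the schedule and the appendix, so the SWD and DRS would not be collected. An analysis plan can say how to score a form, but it cannot supply answers to questions that were never put.

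The wording of the two regret items adds to this. Each joins regret to one particular reason, so the form has no plain measure of whether a woman regrets taking part. Regret is named in the objective and in the endpoint. Section 8.4 also plans yearly reviews of the socio-psychological endpoints by the steering committee and the Ethics and Data Monitoring Committee. As scheduled, those reviews would have item responses on regret but no score from the scale that section 1.1.24 names.

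**Working it through.** No sample size, power or event count enters this point. The check is a comparison of passages and a count of items.

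**Step 1: what section 1.1.24 requires.** The SWD has 6 items and the DRS has 5, both figures from that section. Together: 6 + 5 = 11 items.

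**Step 2: what is scheduled.** Table 1 and the schedule of activities provide one Satisfaction form at M12 and M48. Appendix 4 gives its length as 7 items, and the printed list does contain 7.

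**Step 3: the 7 items sorted by content.**

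| Content | Items | Count | Length of the named scale |
|---|---|---|---|
| Whether joining was a good decision | 1 | 1 | SWD: 6 |
| Regret attributed to follow-up that differed from expectation | 2 | 1 | DRS: 5 (items 2 and 3 together) |
| Regret attributed to more anxiety than expected | 3 | 1 | see row above |
| Study documents, staff explanations, web platform | 4 to 7 | 4 | neither |

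The total is 1 + 2 + 4 = 7. At most 1 + 2 = 3 items bear on the two constructs, against the 11 items of the named scales.

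**Step 4: can either scale be scored?** A 6-item score cannot be built from one related item, nor a 5-item score from two. This follows from the lengths alone. It does not depend on the wording of the SWD or DRS, which the protocol does not print.

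**Step 5: what the two regret items can show.** Agreement with item 2 or item 3 signals regret for that reason. Disagreement with both has two readings: the woman has no regret, or she has regret for a reason that neither item names, such as having learned her risk level. The form does not separate these directly. Item 1 states no cause and helps in part, but it asks whether the decision was good and does not ask about regret.

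**Step 6: does another passage reconcile the two?** Section 1.1.24 allows dedicated questionnaires for very specific purposes and gives satisfaction with particular documents as an example. That could cover items 4 and 5. It does not cover decisional regret, for which the same section names a scale.

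**The case against.** The strongest reply is that the endpoint names constructs and not scales. Section 3.2.2 refers to Table 1, and the Table 1 form has a decision item and two regret items on a 5-point scale. Satisfaction and regret can therefore be summarised item by item, and Appendix 4 mentions tests of proportions and chi-square tests for comparing the arms. The SWD and DRS appear only in the rationale section. The 7 items also derive from a questionnaire described as validated, and scoring rules may properly sit in an analysis plan that is not at hand.

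Much of this stands. It would be wrong to say that the endpoint cannot be analysed; what cannot be formed is the SWD score and the DRS score. The reply does not remove the contradiction, because section 1.1.24 commits to those scales and relies on their measurement properties. Validation of another questionnaire, before its items were selected and modified, does not make this form an SWD or a DRS.

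A reader might also infer four stronger things that the documents do not support:

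- **That a woman with regret for another reason is forced to disagree with both regret items.** The response scale has a neutral option, and she can also disagree with item 1.
- **That the form misses regret over receiving less screening.** Item 2 concerns follow-up that differed from what was expected, which plausibly includes fewer examinations than expected.
- **That regret is among the harms the protocol lists.** Section 1.1.16 refers only in general terms to negative patient-reported outcomes, and sections 6.2.1 and 12.2 do not name regret. It appears in the psycho-social objective and endpoint.
- **That none of the SWD or DRS items is on the form.** The protocol does not print those scales, so item-level overlap cannot be checked. Only the lengths and the absence of the scales by name can be.

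**Conclusion.** The contradiction is real. Section 1.1.24 promises two scales totalling 11 items, and the collection documents provide one 7-item form in which at most 3 items touch the two constructs. Neither named scale can be scored, and responses that are not requested at M12 and M48 cannot be recovered by a later analysis rule.

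The absence of a regret item without a fixed cause makes disagreement with items 2 and 3 ambiguous. Some under-recording of regret is possible, but this is an inference from the wording. The documents give no basis for its size, or for saying that it would favour one arm.

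The scope is limited to one component of a non-key secondary endpoint. The primary non-inferiority analysis and the key secondary superiority analysis are unaffected. The conclusion assumes that Table 1, the schedule and Appendix 4 are the complete list of what women are asked about satisfaction and regret. It is worth correcting because the correction is cheap and has to be in place before the forms are answered.

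**What to change.** Add the SWD (6 items) and the DRS (5 items) to Table 1, the schedule of activities and Appendix 4, at M12 and M48 in both arms. Keep items 4 to 7 of the present form as a separate measure of experience with the information, explanations and platform. The cost is 11 short items at two existing online contacts. The downside is a slightly longer questionnaire and a little more burden for participants.

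If the sponsor does not want the added items, it should remove the SWD and DRS from section 1.1.24 and define satisfaction and regret on the 7-item form: which items represent each construct and how they are summarised. This costs only text, but it gives up the named scales and leaves the ambiguity of items 2 and 3 in place. With either choice, section 1.1.24, Table 1, the schedule and Appendix 4 should agree. The list that opens Appendix 4 should also include the satisfaction form, which it now omits although Table 1 has it. The same edit should state whether the adapted Sat-35 in section 1.1.24 is still intended, since Appendix 4 does not mention it.
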